## **10. Measurement of Effect**

### **10.1 Progression-Free Survival**

PFS will be defined as the time from first study treatment to the point of either radiographic progression of malignancy by RECIST 1.1 criteria or death. Death will be considered clinical progression if the cause of death is felt to be due to the underlying malignancy (vs due to toxicity or a non-malignancy related cause such as accident). Median PFS will be estimated using the Kaplan-Meier method.

The proportion of subjects without progression (as defined above) at 12-months after start of study treatment will constitute the 12-month PFS rate, which is the primary endpoint of this study.

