The potential adverse effects (AEs) of the systemic therapy regimen of cisplatin or carboplatin plus etoposide together with durvalumab were reported in the results of the CASPIAN study (see Appendix A). Specifically, AEs of any cause and grade occurred in 98% of subjects treated with durvalumab plus platinum-etoposide, while 62% of those in this study arm developed any grade 3 or 4 AE, the most common of which were neutropenia and anemia. Only 9% of subjects developed an AE that lead to discontinuation of therapy, however. Deaths due to AE of any cause occurred in 5% of subjects, similar to that in the standard platinum-etoposide group. Immune-mediated AEs (ImAEs) occurred in 20% of subjects treated with durvalumab plus platinum-etoposide, with only 5% being grade 3 or 4. The most common ImAEs were hypo- and hyperthyroidism. Death due to ImAE occurred in <1% of subjects (1 subject – due to hepatotoxicity).

A primary objective of this study is to evaluate the risks of adding non-ablative radiation to the above treatment regimen. Potential risks which the study will focus on will be an increase in ImAEs (other than thyroid dysfunction, which is generally easily managed), and an increase in radiation-related AEs, specifically pneumonitis, pericarditis, esophagitis, rib fracture, and hemoptysis. The reported rates of pneumonitis after SBRT requiring intervention range from 0-29%, with an uncommon occurrence of severe ( $\geq$  grade 3) pneumonitis. Reported cardiac events associated with SBRT occur in 0-7.9% of treated patients. Chest wall related toxicities after SBRT include skin toxicity (1.2-14%), rib fracture (5%) and chronic chest wall pain (5-25%) and are usually associated with peripherally located lung tumors. Esophageal injury ranging from mild esophagitis to stricture, perforation, and/or fistula formation has been reported to occur in 12% of patients treated with SBRT. Finally, with standard fractionation schemes fatal hemoptysis secondary to aortic damage, rupture, aneurysm, or aortic dissection may occur in up to 5.7% of patients, particular for those that receive a maximum composite dose to 1cm^3 of the aorta  $\geq$  120Gy (25% rate of grade 5 toxicity) versus < 120Gy (0% rate of grade 5 toxicity). Similar cases have been reported with

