## **10.2 Overall Survival**

OS will be defined as the time from first study treatment to the time of death from any cause. Median OS will be estimated using the Kaplan-Meier method. The proportion of subjects still alive at 12-months after start of study treatment will constitute the 12-month OS rate.

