#### **12.4.1 Analysis of Primary Endpoints**

The primary endpoint of the 12-month PFS proportion will be calculated and a 95% confidence interval will be estimated via binomial proportions. A one-group chi-square test will be used to compare the 12-month PFS proportion with a historical 12-month PFS proportion of 18%. PFS will also be estimated using the Kaplan-Meier method, and 95% confidence intervals for PFS estimates (including median PFS) will be calculated using Greenwood's formula.

The primary endpoint of safety will be described by the incidence of  $\geq$  Grade 3 toxicities definitely or probably related to the treatments given (i.e. radiation, immunotherapy, and/or chemotherapy), as reported and graded by NCI CTCAE version 5.0.

Full descriptive analysis of safety will also be conducted (e.g. AEs considered causally related to treatment regimen, serious AEs, AEs leading to discontinuation).

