#### **13.2.2 Deaths**

All deaths that occur during the study treatment period, or within the protocol-defined follow-up period after the administration of the last dose of study drug, must be reported as follows:

- Death clearly resulting from disease progression should be reported and documented in the CRF, in the Statement of Death page. It should not be reported as an SAE.
- Where death is not due (or not clearly due) to progression of the disease under study, the AE causing the death must be reported.
- The report should contain a comment regarding the co-involvement of disease progression, if appropriate, and should assign main and contributory causes of death.
- Deaths with an unknown cause should always be reported as an SAE. It should also be documented in the Statement of Death page in the CRF.

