**Table 4: Adverse events of any cause (safety population)**

Table S5: Treatment-related adverse events as assessed per the investigator (safety population)

	Durvalumab + EP (n=265)		EP (n=266)	
	Any grade	Grade 3 or 4	Any grade	Grade 3 or 4
Any treatment-related event, n (%)	237 (89%)	121 (46%)	240 (90%)	138 (52%)
Any treatment-related serious event, n (%)	35 (13%)	25 (9%)	50 (19%)	45 (17%)
Any treatment-related event leading to discontinuation, n (%)*	15 (6%)	3 (1%)	13 (5%)	4 (2%)
Any treatment-related event leading to death, n (%)†	5 (2%)	—	2 (1%)	—
Treatment-related adverse events with an incidence of $\geq 5\%$ in any grade category or events of grade 3 or 4 with an incidence of $\geq 2\%$ in either arm, n (%)‡				
Neutropenia	104 (39%)	61 (23%)	116 (44%)	86 (32%)
Anaemia	85 (32%)	21 (8%)	103 (39%)	38 (14%)
Alopecia	74 (28%)	3 (1%)	85 (32%)	2 (1%)
Nausea	74 (28%)	0	75 (28%)	5 (2%)
Thrombocytopenia	37 (14%)	14 (5%)	48 (18%)	24 (9%)
Vomiting	32 (12%)	0	38 (14%)	2 (1%)
Decreased appetite	33 (12%)	1 (<1%)	35 (13%)	1 (<1%)
Leucopenia	36 (14%)	15 (6%)	32 (12%)	14 (5%)
Fatigue	30 (11%)	2 (1%)	36 (14%)	3 (1%)
Asthenia	27 (10%)	2 (1%)	31 (12%)	2 (1%)
	Durvalumab + EP (n=265)		EP (n=266)	
	Any grade	Grade 3 or 4	Any grade	Grade 3 or 4
Neutrophil count decreased	24 (9%)	16 (6%)	28 (11%)	17 (6%)
Constipation	23 (9%)	0	24 (9%)	0
Diarrhoea	17 (6%)	2 (1%)	15 (6%)	2 (1%)
Febrile neutropenia	15 (6%)	13 (5%)	17 (6%)	17 (6%)
White blood cell count decreased	12 (5%)	4 (2%)	17 (6%)	6 (2%)
Platelet count decreased	14 (5%)	4 (2%)	13 (5%)	6 (2%)
Paraesthesia	14 (5%)	0	11 (4%)	0
Hypothyroidism	23 (9%)	0	0	0
Hyperthyroidism	22 (8%)	0	0	0
Lipase increased	10 (4%)	8 (3%)	2 (1%)	1 (<1%)

Data cutoff date: March 11, 2019. Listed are all adverse events assessed by the investigator as possibly related to any study treatment that occurred during the treatment period and up to 90 days after the last dose of durvalumab or EP or up to the start of any subsequent therapy (whichever occurred first). \*Includes patients who permanently discontinued at least one study drug. †Treatment-related adverse events leading to death in the durvalumab plus EP arm were cardiac arrest, dehydration, hepatotoxicity, pancytopenia, and sepsis in one patient each. Treatment-related adverse events leading to death in the EP arm were pancytopenia and thrombocytopenia/haemorrhage in one patient each. ‡The events are listed in descending order of frequency across both treatment arms. EP=platinum-etoposide.

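### Section 10.1 contradicts itself on whether a death from toxicity or another non-cancer cause is a PFS event; taken literally, the 12-month primary endpoint does not count it as a failure

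*Combined protocol and SAP*

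**What the plan says.** Three statements in Section 10.1 matter.

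1. PFS runs from first study treatment to "either radiographic progression of malignancy by RECIST 1.1 criteria or death". Cause of death is not restricted.
2. "Death will be considered clinical progression if the cause of death is felt to be due to the underlying malignancy (vs due to toxicity". The same parenthesis also sets aside causes unrelated to the malignancy, with accident as the example. Only cancer deaths are classed as progression.
3. "The proportion of subjects without progression (as defined above) at 12-months after start of study treatment will constitute the 12-month PFS rate". This is named as the primary endpoint.

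Section 12.4.1 analyses that endpoint as a binomial proportion with a one-group chi-square test against 18%, and adds that "PFS will also be estimated using the Kaplan-Meier method". It gives no event, censoring or death rule for either analysis. Section 12.1 gives the design figures and no event rule.

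Two other sections bear on the wording. Section 10.2 is explicit for survival: "OS will be defined as the time from first study treatment to the time of death from any cause". Section 13.2.2 foresees deaths that cannot be attributed: "Deaths with an unknown cause should always be reported as an SAE". Section 10.1 has no rule for scoring those.

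**The concern.** Under the first sentence of 10.1, a toxic death before RECIST progression is a PFS event. Under the second and third, the same subject has not progressed and so is not a failure at 12 months. Two analysts could follow the protocol faithfully and report different primary results. The same death could also be an event in the Kaplan-Meier curve and a non-failure in the primary test.

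On the literal reading the error runs one way. Each toxic or other non-cancer death before progression raises the observed 12-month rate, so harm from the regimen under test counts in favour of its efficacy. The safety co-primary endpoint and 12-month OS would show such deaths, but neither corrects the PFS test. The trial is open-label and single-arm, 10.1 does not say who judges the cause of death, and the scoring choice could be made after outcomes are known.

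**Working it through.** **Inputs.** Null rate 18%, alternative 38%, two-sided 0.05, n = 34, 80% power, 95% CI half-width 16.3 points (Section 12.1). Historical durvalumab plus platinum-etoposide arm, n = 265: 13 deaths from adverse events of any cause (Appendix A, Table 4; Section 2.5.1 says "Deaths due to AE of any cause occurred in 5% of subjects") and 5 treatment-related deaths (Appendix A, Table S5: "Treatment-related adverse events leading to death in the durvalumab plus EP arm were cardiac arrest, dehydration, hepatotoxicity, pancytopenia, and sepsis in one patient each").

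**Step 1: the plan's own figures.**
- n = [1.960·√(0.18·0.82) + 0.842·√(0.38·0.62)]² / 0.20² = 33.7, rounded up to 34.
- Power at n = 34 is 80.3%.
- Half-width = 1.960·√(0.38·0.62/34) = 0.163.

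All three reproduce. The sample-size statement is sound; the defect is in the endpoint definition.

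**Step 2: where the test rejects.** z = (x/34 − 0.18)/√(0.18·0.82/34), with standard error 0.0659.

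| Event-free at 12 months | Proportion | z | Two-sided p |
|---|---|---|---|
| 9/34 | 26.5% | 1.286 | 0.199 |
| 10/34 | 29.4% | 1.732 | 0.083 |
| 11/34 | 32.4% | 2.178 | 0.029 |

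Each reclassified death moves the estimate by 1/34 = 2.9 points. One can turn 10/34 into a positive result; two can turn 9/34 into one.

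**Step 3: false-positive rate on the literal reading.** Let the true proportion alive and progression-free be 18%, and let d be the proportion dying of a non-cancer cause before progression and before month 12. If those deaths are scored as non-failures, the success probability becomes 0.18 + 0.82d when d applies only to the 82% who would otherwise fail, or 0.18 + d when d is added in full. The upward false-positive rate is the binomial P(X ≥ 11) with n = 34.

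| d | 0.18 + 0.82d | P(X ≥ 11) | 0.18 + d | P(X ≥ 11) |
|---|---|---|---|---|
| 0 | 0.1800 | 3.2% | 0.1800 | 3.2% |
| 5/265 = 1.9% | 0.1955 | 5.4% | 0.1989 | 6.0% |
| 13/265 = 4.9% | 0.2202 | 10.9% | 0.2291 | 13.5% |

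**Step 4: how likely such deaths are among 34.** Expected number 34d = 0.6 and 1.7. P(at least one) = 1 − (1 − d)^34 = 48% and 82%. P(at least two) = 1 − (1 − d)^34 − 34d(1 − d)^33 = 13% and 50%.

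**Step 5: a milder branch.** Suppose such deaths were instead dropped as not evaluable and 34 evaluable subjects were still reached. The success probability is then 0.18/(1 − d), which is 0.1835 and 0.1893, and P(X ≥ 11) is 3.6% and 4.4%. If the denominator shrinks instead, 10/33 gives p = 0.066 and 10/32 gives p = 0.051.

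**The case against.** The strongest reply is that 10.1 is ambiguous rather than contradictory. The first sentence defines PFS, the tested quantity is called the 12-month PFS rate throughout, and the phrase pointing back to the definition could mean that first sentence. The second sentence would then only label the type of event; it never says that other deaths are successes. This reading is possible. But it leaves the second sentence with no effect on the endpoint, although that sentence expressly sets toxicity deaths apart from progression, and the text does not choose between the readings.

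A second reply is that the larger error rates assume a non-cancer death is scored as a success. If it were excluded, the inflation would be small (3.6% to 4.4%), and one or two exclusions would not make 10 successes significant. That arithmetic is right. However, nothing in 10.1 states an exclusion, the evaluability wording in Sections 12.2 and 12.6.2 does not supply one for PFS, and an excluded death still does not count as a failure.

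Third, the death rates are rough. Appendix A counts deaths up to 90 days after the last dose or until subsequent therapy, so some may follow progression. Some of the 13, such as the sudden deaths and the pulmonary embolism, could be attributed to the cancer. This stands: 4.9% is nearer an upper figure for that regimen.

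Fourth, attribution is partly covered elsewhere. Section 13.2.2 asks for main and contributory causes when a death is not clearly due to progression, and Section 13.4 has investigators assess causality of SAEs. This also stands, but those are reporting rules and say nothing about how the death is scored for PFS.

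Finally, this is a pilot, and toxic deaths stay visible in the safety endpoint and OS. True, but the plan still attaches a formal test to the 12-month PFS rate.

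**Conclusion.** The concern holds, and the definition must be fixed before analysis. As written, Section 10.1 lets a toxic or other non-cancer death before RECIST progression escape being a failure in the efficacy co-primary endpoint, and no other section repairs this.

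That one such death can separate a negative trial from a positive one needs only the literal scoring rule and the planned test. The inflation from 3.2% to 5.4–6.0% or 10.9–13.5% is illustrative. It assumes that the deaths are scored as non-failures, that they occur before progression and within 12 months at the historical arm's rates, and that the 18% benchmark counts every death as an event, which the documents do not state. Any additional deaths from radiation are unknown and not included. Under exclusion instead of success the inflation is much smaller, though still upward.

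**What to change.** In Section 10.1, define a PFS event as the first of RECIST 1.1 progression or death from any cause, including unknown cause. Define the 12-month PFS rate as the proportion of subjects alive and progression-free at 12 months. Remove the sentence that limits death to malignancy, or move it to a labelled sensitivity analysis in which only cancer deaths count as events. In Section 12.4.1, state that the binomial test and the Kaplan-Meier estimate use the same event rule.

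The cost is two or three sentences, with no new data, visits or subjects. The sample size of 34, the power of about 80% and the 11/34 cut-off are unchanged. The one downside for the sponsor is that the observed 12-month rate may be slightly lower than under the literal wording.

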## **10.2 Overall Survival**

OS will be defined as the time from first study treatment to the time of death from any cause. Median OS will be estimated using the Kaplan-Meier method. The proportion of subjects still alive at 12-months after start of study treatment will constitute the 12-month OS rate.

## **10.3 Response Criteria**

Response will be assessed based on imaging as per RECIST 1.1 criteria. The Overall Response Rate (ORR) will be calculated by the proportion of subjects achieving a RECISTv1.1 complete or partial response.

# **11. Data Reporting / Regulatory Considerations**

## **11.1 Data Collection**

The data collection plan for this study is to utilize REDCap to capture all treatment, toxicity, efficacy, and adverse event data for all enrolled subjects.

### **11.1.1 REDCap**

REDCap (Research Electronic Data Capture) is a free data management software system that is fully supported by the Weill-Cornell Medical Center CTSC. It is a tool for the creation of customized, secure data management systems that include Web-based data-entry forms, reporting tools, and a full array of security features including user and group based privileges, authentication using institution LDAP system, with a full audit trail of data manipulation and export procedures. REDCap is maintained on CTSC-owned servers that are backed up nightly and support encrypted (SSL-based) connections. Nationally, the software is developed, enhanced and supported through a multi-institutional consortium led by the Vanderbilt University CTSA.

## **11.2 Regulatory Considerations**

### **11.2.1 Institutional Review Board/Ethics Committee Approval**

As required by local regulations, the Investigator will ensure all legal aspects are covered, and approval of the appropriate regulatory bodies obtained, before study initiation.

Before initiation of the study at each study center, the protocol, the ICF, other written material given to the patients, and any other relevant study documentation will be submitted to the appropriate Ethics Committee. Written approval of the study and all relevant study information must be obtained before the study center can be initiated or the IP is released to the Investigator. Any necessary extensions or renewals of IRB approval must be obtained for changes to the study, such as amendments to the protocol, the ICF, or other study documentation. The written approval of the IRB together with the approved ICF must be filed in the study files.

The Investigator will report promptly to the IRB any new information that may adversely affect the safety of the patients or the conduct of the study. The Investigator will submit written summaries of the study status to the IRB as required. On completion of the study, the IRB will be notified that the study has ended.

All agreed protocol amendments will be clearly recorded on a protocol amendment form and will be signed and dated by the original protocol approving signatories. All protocol amendments will be submitted to the relevant institutional IRB for approval before implementation, as required by local regulations. The only exception will be when the amendment is necessary to eliminate an immediate hazard to the trial participants. In this case, the necessary action will be taken first, with the relevant protocol amendment following shortly thereafter.

Once protocol amendments or consent form modifications are implemented at the lead site, Weill Cornell Medicine, updated documents will be provided to participating sites, as applicable. Weill Cornell Medicine must approve all consent form changes prior to local IRB submission.

Relevant study documentation will be submitted to the regulatory authorities of the participating countries, according to local/national requirements, for review and approval before the beginning of the study. On completion of the study, the regulatory authorities will be notified that the study has ended.

#### **11.2.2 Ethical Conduct of the Study**

The Investigators and all parties involved should conduct this study in adherence to the ethical principles based on the Declaration of Helsinki, GCP, ICH guidelines and the applicable national and local laws and regulatory requirements.

This study will be conducted under a protocol reviewed and approved by the applicable ethics committees and investigations will be undertaken by scientifically and medically qualified persons, where the benefits of the study are in proportion to the risks.

#### **11.2.3 Informed Consent**

The investigator or qualified designee must obtain documented consent according to ICH-GCP and local regulations, as applicable, from each potential subject or each subject's legally authorized representative prior to participating in the research study. Subjects who agree to participate will sign the approved informed consent form and will be provided a copy of the signed document.

The initial ICF, any subsequent revised written ICF and any written information provided to the subject must be approved by IRB prior to use. The ICF will adhere to IRB requirements, applicable laws and regulations.

#### **11.2.4 Compliance with Trial Registration and Results Posting Requirements**

Under the terms of the Food and Drug Administration Modernization Act (FDAMA) and the Food and Drug Administration Amendments Act (FDAAA), the Sponsor-Investigator of the trial is solely responsible for determining whether the trial and its results are subject

to the requirements for submission to <http://www.clinicaltrials.gov>. Information posted will allow subjects to identify potentially appropriate trials for their disease conditions and pursue participation by calling a central contact number for further information on appropriate trial locations and trial site contact information.

#### **11.2.5 Record Retention**

Essential documents are those documents that individually and collectively permit evaluation of the study and quality of the data produced. After completion of the study, all documents and data relating to the study will be kept in an orderly manner by the Investigator in a secure study file. Essential documents should be retained for 2 years after the final marketing approval in an ICH region or for at least 2 years since the discontinuation of clinical development of the IP. In addition, all subjects medical records and other source documentation will be kept for the maximum time permitted by the hospital, institution, or medical practice.

### **12. Statistical Considerations**

#### **12.1 Study Design/Endpoints**

One primary aim of this study is to demonstrate that the addition of radiation to chemotherapy and immunotherapy is associated with an improvement in 12-month PFS from 18% historical control to approximately 38% with the addition of radiation. With a sample size of 34 patients receiving chemotherapy/immunotherapy plus radiation, a one-group chi-square test will have 80% power to detect the difference between a null hypothesis 12-month PFS proportion of 18% (i.e., historical control) and an alternative hypothesis 12-month PFS proportion of 38% (i.e., chemotherapy + immunotherapy + radiation), with a 0.05 two-sided significance level. As well, a sample size of 34 patients will allow a two-sided 95% confidence interval for the expected 12-month PFS proportion (38%) to be constructed to be within  $\pm 16.3\%$  of the observed 12-month PFS proportion.

The second primary aim of this study is to evaluate the safety of combining carboplatin + etoposide chemotherapy, durvalumab immunotherapy, and non-ablative radiation to one or more sites of disease. Due to this, we propose a safety run-in for the first 10 subjects. If there is a 30% or greater incidence of grade 3 or higher toxicities with the proposed treatment regimen, specifically from radiation therapy (with focus on pneumonitis, pericarditis, esophagitis, rib fracture, or hemoptysis) or immune-mediated adverse events (other than thyroid dysfunction), then the radiation regimen will be switched to 5 Gy radiation per day for 5 days. If there is still a 30% or greater incidence of grade 3 or higher toxicities from radiation therapy or immune-mediated adverse events among the subsequent 10 subjects, then the study will be terminated. If this does not occur, then accrual will continue until 34 total subjects are evaluable.

